Nitrous oxide is an inhaled analgesic that is used in pediatric and adult populations for ambulatory procedures, and is largely viewed as effective and safe. Nitrous oxide also produces a dissociative euphoria and amnesia that could potentially improve patients' anxiety and experience of care during painful or anxiety provoking procedures. We have used patient self-administered nitrous oxide (SANO) in our ambulatory clinic at BIDMC for men undergoing prostate biopsies with good effect and no significant complications. SANO may offer an appealing option for patients who are reluctant to undergo an initial UDS or for those who have not tolerated the study in the past. What we do not know is whether a UDS performed under the influence of SANO will give study results that are accurate and reproduce the bladder function of the patient during their daily routine. In a pediatric population, both ketamine and midazolam have been shown to provide satisfactory sedation without impacting UDS values (Thevaraja, 2012); however, sedation with propofol does negatively impact outcome values (Merguerian, 2006). No studies to date assess whether the administration of SANO will negatively impact UDS results. It is possible that SANO will perform better than ketamine or midazolam, as it is anticipated SANO will reduce anxiety and perception of pain without causing a sedative effect.

We propose a pilot study with 25 patients (14 randomized) to compare the impact of SANO vs Oxygen on UDS parameters of patients undergoing routine UDS. Study procedures will take place in the Clinical Research Center (ST 802, Gryzmish 8). Our primary aim will be to assess whether SANO has any adverse effects on routinely measured UDS variables. We will assess whether

periprocedural SANO negatively impacts operator productivity or increases the difficulty in performing the UDS. A secondary aim will be to assess patient perceived pain and anxiety related to catheter placement and experience of SANO during the UDS.

Specific Aims:

Aim 1: To demonstrate that Self-Administered Nitrous Oxide (SANO) at the time of Urodynamic Study (UDS) does not significantly impact outcome variables during the study.

Hypothesis 1.1: Administration of periprocedural SANO will not impact core UDS outcomes of “Bladder Capacity”, “Maximum Flow Rate”, and “Maximum Detrusor Pressure”

Hypothesis 1.2: Administration of periprocedural SANO will not significantly lengthen the time of the procedure

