#### Please note:

In our original study protocol, we had based our sample size calculation on a study by Jeon et al. However, as the inter-class correlation was not reported in the study by Joen et al., using their study increases our risk of a type 2 error. In light of this, we performed a literature review of all studies comparing cystometric capacity on repeat cystometry to identify a study that also reports inter-subject correlation. Using the maximum cystometric capacity (MCC) by Broekhuis et al., with an interclass correlation coefficient of 0.86, the sample size calculation to detect clinically relevant a priori difference in 50mL with a power of 82% was 16 patients total. The resulting sample size is less than the amount recruited in our study (19), thus the risk of a type 2 error is less than 20%. The below statistical analysis reflects our updated design.

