### *Outcomes*

An intention-to-treat analysis was performed on 19 participants. MCC was measured as the primary outcome. Secondary outcomes included patient-reported pain and anxiety measured at baseline and immediately before maximum capacity during each UDS run using the Visual Analog Scale for Pain (VAS-P; range 0-10) and the Visual Analog Scale for Anxiety (VAS-A; range 0-10).

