### *Statistical Analysis*

Bivariate analyses were performed to compare UDS outcomes, pain and anxiety scores, and operator-reported outcomes during SANO and Oxygen runs. Paired Wilcoxon signed rank sum test and McNemar's chi-squared Tests were used for continuous and categorical variables, respectively. For two variables (Patient Responsiveness during UDS and Observed Patient Procedure Tolerance), there were no categorical responses for the treatment arms. Therefore, the substitution of zero with a value of 0.5 was used to satisfy the chi-squared conditions. Subgroup analysis was performed to compare key UDS outcomes between treatments for patients randomized to either Oxygen or SANO on the 1st run. Additionally, a sensitivity analysis was performed comparing UDS outcomes between treatment groups for the 1st UDS run only. An alpha of 0.05 and 95% confidence intervals (CI) were used as criteria for statistical significance. For continuous data, a pairwise version of the Hodges-Lehman Median Difference method was used to estimate a pseudo-median difference and corresponding 95% CI. Data were collected and stored using REDCap electronic data capture tools hosted at Beth Israel Deaconess Medical Center. Analyses were performed using Microsoft Excel (v16.66.1), R (v4.3.0), and SPSS (v29.0).

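### Aim 1 seeks to show that SANO leaves UDS results unchanged, but the SAP has only a difference test and never reads its confidence interval against its own 50 mL threshold

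*SAP*

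**What the plan says.** The protocol (B1, Specific Aims) words Aim 1 as an absence-of-effect objective: "To demonstrate that Self-Administered Nitrous Oxide (SANO) at the time of Urodynamic Study (UDS) does not significantly impact outcome variables during the study". Hypothesis 1.1 is blunter: "Administration of periprocedural SANO will not impact core UDS outcomes of" bladder capacity, maximum flow rate and maximum detrusor pressure.

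The SAP (Outcomes) states "MCC was measured as the primary outcome" and "An intention-to-treat analysis was performed on 19 participants". Under Statistical Analysis it gives the tests: "Paired Wilcoxon signed rank sum test and McNemar's chi-squared Tests were used for continuous and categorical variables, respectively". It also plans an interval: "a pairwise version of the Hodges-Lehman Median Difference method was used to estimate a pseudo-median difference and corresponding 95% CI". The criterion applied to both is "An alpha of 0.05 and 95% confidence intervals (CI) were used as criteria for statistical significance".

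The 50 mL figure appears once, in the SAP's opening note on sample size: "clinically relevant a priori difference in 50mL with a power of 82% was 16 patients total". The same note gives a correlation of 0.86 between repeat fills and says that, with 19 patients recruited, the type 2 error is below 20%. The SAP text available for this review contains no equivalence margin, no equivalence test and no rule comparing the interval with 50 mL.

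**The concern.** A difference test can reject the hypothesis of no difference; failing to reject it does not establish that hypothesis. When the goal is to show no effect, the usual safeguard is reversed: a smaller sample or noisier measurement makes p>0.05 more likely, and so favours the result the investigators hope for.

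What is at stake is the main clinical message, namely whether a urodynamic study done under SANO can be trusted. If the only benchmark is significance, a wide interval that includes shifts beyond 50 mL and a narrow one that excludes them are classified alike, provided both include zero.

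**Working it through.** **Inputs.** From the SAP: 50 mL, 16 patients, 82% power, correlation 0.86, 19 analysed, alpha 0.05. Not given: the SD, the test behind the sample size, and its sidedness. I assume a two-sided paired t-test, as a stand-in for the signed-rank test, and normal paired differences.

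**Step 1: the plan's own figure.** Without an SD, 16 patients cannot be reproduced independently, only back-solved. Power is the probability that a noncentral t with n−1 degrees of freedom and noncentrality δ√n/σ falls beyond ±t(0.975, n−1). Setting n = 16, δ = 50 and power = 0.82 gives σ = 65.0 mL (noncentrality 50 × 4 / 65.0 = 3.08; critical value 2.131). The implied per-run SD is 65.0 / √(2 × (1 − 0.86)) = 65.0 / 0.529 ≈ 123 mL.

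Other conventions give σ of 69.6 (two-sided normal approximation), 74.5 (one-sided t) or 78.1 (one-sided normal). Allowing for 95.5% signed-rank efficiency gives about 63. The results below therefore cover a range of SDs.

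**Step 2: the difference test at n = 19.** With σ = 65.0 the noncentrality is 50 × 4.359 / 65.0 = 3.35 and the critical value is 2.101. Power is 88.7%, so a true 50 mL shift is non-significant in 11.3% of trials. This agrees with the SAP's statement of type 2 error below 20%, provided σ is about 65.

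**Step 3: an interval rule at n = 19.** No clinically relevant effect is concluded only if the CI lies wholly within −50 to +50 mL. The 90% CI corresponds to two one-sided 5% tests. At σ = 65 its expected half-width is about 1.734 × 65.0 / 4.359 = 25.9 mL; for the 95% CI it is about 2.101 × 65.0 / 4.359 = 31.3 mL.

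| SD of differences (mL) | True shift 50: p>0.05 | True shift 50: 90% CI inside ±50 | True shift 0: 90% CI inside ±50 | True shift 0: 95% CI inside ±50 |
|---|---|---|---|---|
| 50 | 2% | 5% | 99% | 97% |
| 65 | 11% | 5% | 89% | 77% |
| 70 | 16% | 5% | 82% | 68% |
| 80 | 27% | 5% | 67% | 47% |
| 100 | 46% | 5% (4.5%) | 35% | 15% |

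The second column rises with the SD: the noisier the data, the more often a true 50 mL shift passes as non-significant. The third column does not exceed 5%. The cost appears in the last two columns, where noisy data lead to an inconclusive result. With no true effect, the difference test returns p>0.05 in 95% of trials whatever the SD.

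**Step 4: how often the two readings part.** At σ = 65 and a true shift of 25 mL, about 64% of trials are non-significant. In about 31% of all trials the result is non-significant and the 95% CI still extends beyond ±50 mL.

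**The case against.** The case on the other side is substantial.

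- **The SAP never says that p>0.05 proves no effect.** This is correct, and a reader should not attribute that statement to it. The reading is an inference from an aim phrased in terms of significance, a sole criterion of significance, and reassurance about type 2 error. What stands is that nothing in the text rules the inference out.
- **The materials for a sound reading are already planned.** A paired estimate with a 95% CI is specified and 50 mL is named. This stands: the gap is in the decision rule, not in data or estimation.
- **The study is a pilot, and B1 also describes the primary aim as assessing whether SANO has adverse effects on UDS variables.** A difference test suits that detection question. The documents contain both framings, but Aim 1 and Hypothesis 1.1 remain claims of no effect.
- **Power was considered.** On the back-solved SD, type 2 error at 50 mL is about 11%. However, planned power rests on an unstated SD and does not show what the observed interval excludes.
- **Smaller shifts can be made to look alarming.** At σ = 65, shifts of 20.6, 30 and 40 mL are non-significant in 74%, 52% and 28% of trials. These are not errors against a 50 mL threshold, and the ±50 mL rule would itself accept 60%, 36% and 16% of them. The 20.6 mL is a repeat-fill difference from the superseded calculation, not a SANO effect. The fair contrast is at 50 mL: 11% against 5%.

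A reader might also infer that the intention-to-treat set biases the result towards no difference, because the protocol allows the mask to be removed. The documents do not say how often this happened or how such runs were measured, so the point cannot be sized and is not relied on here.

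**Conclusion.** The mismatch is real and confined to Aim 1. Under the stated criterion, a non-significant MCC comparison cannot support a conclusion that SANO has no impact. At the SAP's own threshold, a true 50 mL shift goes undetected in about 11% of trials of 19 patients if the SD of paired differences is 65 mL, 27% at 80 and 46% at 100. An interval rule keeps the corresponding error at or below about 5%.

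These sizes rest on an SD the SAP does not state, on two-sided testing, and on a paired t standing in for the signed-rank test.

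It would be tempting to conclude that the trial is too small to show equivalence. The documents do not support that: at SD 65, 19 patients give about 89% power for the ±50 mL rule with a 90% CI, or 77% with the 95% CI. Whether the sample suffices depends on the observed SD. Difference tests remain suitable for the pain and anxiety aim.

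**What to change.** In the SAP and the report:

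1. State that p>0.05 is not evidence of no effect on UDS outcomes.
2. Conclude that SANO has no clinically relevant effect on MCC only if the CI for the SANO minus Oxygen Hodges-Lehmann difference lies wholly within −50 to +50 mL. Use the 90% CI (two one-sided 5% tests) or, as a stricter reading, the 95% CI already planned. Say which one governs. Otherwise report the result as inconclusive.
3. Label 50 mL as a post hoc equivalence margin unless an earlier record shows that it was prespecified for that use. The SAP is written after recruitment and analysis, and calls 50 mL a priori only as a difference to detect.
4. For maximum flow rate and maximum detrusor pressure, report the estimate and CI without claiming no impact, unless a margin is stated and justified.

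The cost is a few sentences and at most one extra interval; no patients or measurements are added. The downside is that the no-effect conclusion becomes harder to reach if the observed SD is large: about 67% power at SD 80 and 35% at SD 100, even when SANO truly has no effect.

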Study Protocol Cover Page

Study Protocol

ID: 2022P-000826

A Pilot Study to Assess Effects of Self-Administered Nitrous Oxide (SANO) on Urodynamic Study (UDS) Parameters

Please note: the Statistical Design included in this Protocol has been updated, and is included separately.

PART B STUDY DESCRIPTION

TITLE OF PROTOCOL	A Pilot Study to Assess the Effects of Self-Administered Nitrous Oxide (SANO) on Urodynamic Study (UDS) Parameters
Principal Investigator	[name] PhD

B1. PURPOSE OF PROTOCOL

A Urodynamic Study (UDS) is a diagnostic procedure commonly performed by Urologists in the ambulatory setting to diagnose urinary dysfunction. A UDS is generally considered to have low morbidity, but patients may find it uncomfortable and anxiety provoking, partly because the study involves placing both a urethral and abdominal pressure catheter. The abdominal pressure catheters are placed in the rectum (for men and children) and the vagina (for women). Additionally, there are EMG electrodes placed at the anal sphincter, and in some patients (primarily children) these are needle electrodes. In adults, studies show that after a UDS, 15-26% of patients would not elect to undergo the UDS procedure again (Yokoyama, 2005). In children, distress rates can be as high as 61-71% during UDS (Herd, 2006). There have been multiple studies that have looked at ways to decrease the anxiety and discomfort experienced by patients during a UDS, including use of music, videos, and dimming of lights, all with varying effect. There are also studies that have looked at the use of medications such as ketamine or midazolam to reduce the pain and anxiety during UDS; however, in principle, UDS should not be performed when the patient is sedated as there is constant verbal feedback that is required throughout the testing process.

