Confirmation of a patient's eligibility and completed informed consent will be documented in REDCap before proceeding with study procedures. Then, patients will complete the Brief Pain Inventory (see attached) via REDCap questionnaire that is sent to the patient's email. The BPI is a well-validated measure that assesses intensity of current pain and interference of pain in the patient's life (Dworkin, 2005). If the patient does not complete the BPI electronically before the day of procedure, they will be offered the opportunity to complete it on the day of their procedure prior to the UDS.

Randomization

A UDS is comprised of two phases: a filling phase and a voiding phase. For the purposes of our study, subjects will undergo two “runs”, one with SANO and one with Oxygen.

Subjects will be randomized to either:

- Group 1: First run with SANO, second run with Oxygen
- Group 2: First run with Oxygen, second run with SANO

The results of the randomization will not be disclosed to patients as part of the study (patient-blinded), or to the operator of the UDS (provider-blinded). The randomization module in REDCap will be used to randomize subjects between the two groups.

The catheters will be placed before the first run, and left in place through the second run (that is, the catheters will not be changed between the two runs). All subjects will receive SANO during catheter placement. The UDS will be performed by a BIDMC advanced care practitioner according to usual clinical practice. It is standard-of-care for patients to undergo two complete UDS runs:

- First run: Filling phase, voiding phase (~8 minutes)
- Second run: Filling phase, voiding phase (~8 minutes)

Therefore, we do not believe the utilization of two runs to be a significant increase in burden on the patient.

Pre-procedure Evaluation

On the day of the UDS, the patient will be brought to the exam room where pre-procedure vitals are obtained. The six-item State Trait Anxiety Inventory and the six-item Pain Catastrophizing Scale will be administered to assess patient’s baseline pain and anxiety levels. Information of inhaled gas administration and how to self-administer will be explained to the patient using templated verbal instructions. It will be emphasized that if at any point during the procedure, the patient feels uncomfortable with the inhaled gas, the team will help remove the mask.

Periprocedural Intervention

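### The planned UDS comparisons measure net group shift only, so they cannot show that an individual patient's result agrees between the SANO and Oxygen runs

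*SAP*

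**What the plan says.** **Purpose.** Protocol B1 opens: "A Urodynamic Study (UDS) is a diagnostic procedure commonly performed by Urologists in the ambulatory setting to diagnose urinary dysfunction". It then gives the open question as "whether a UDS performed under the influence of SANO will give study results that are accurate and reproduce the bladder function of the patient". Aim 1 is to demonstrate that SANO "does not significantly impact outcome variables during the study", and Hypothesis 1.1 names three core outcomes: bladder capacity, maximum flow rate (Qmax) and maximum detrusor pressure (Pdet max).

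**Design.** Under Randomization (protocol B3), each patient has two runs in random order, "one with SANO and one with Oxygen". There is no repeat of either gas.

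**Analysis.** In the SAP, "MCC was measured as the primary outcome" (maximum cystometric capacity), in 19 participants. Continuous variables are compared by the paired Wilcoxon test and categorical ones by McNemar's test. For the size of the effect, "a pairwise version of the Hodges-Lehman Median Difference method was used to estimate a pseudo-median difference and corresponding 95% CI". The SAP adds a subgroup analysis by which gas came first and a sensitivity comparison restricted to the first run. The stated criterion is significance at 0.05 with 95% CIs.

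**The 50 mL.** It appears only in the SAP's opening note, in "the sample size calculation to detect clinically relevant a priori difference in 50mL", with 82% power, 16 patients and a correlation of 0.86 between repeat measurements. The SAP does not use it as an equivalence margin or as a tolerance for one patient.

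**The concern.** A UDS is read in one patient at a time. A pseudo-median of paired differences locates the centre of those differences and says little directly about their spread. If capacity rises in some patients and falls in others, the centre can sit near zero while few patients have similar results on both runs. McNemar's test has the same property for categorical findings, because switches in opposite directions offset each other. The first-run comparison is between patients and cannot speak to agreement within a patient.

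The SAP text available contains no limits of agreement, no count of patients whose result changed and no paired tabulation of findings. Pairing is used to gain precision, but the within-patient information it carries is not reported. Because Aim 1 is framed as the absence of a significant impact, a non-significant test could be read as an answer to the question in protocol B1, when it bears only on the average.

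**Working it through.** **1. The SAP's own sample size.** Inputs from the SAP note: n = 16, difference 50 mL, power 82%, correlation 0.86. Alpha 0.05 is from Statistical Analysis; two-sided is assumed. No SD is given, so the figure of 16 can be neither reproduced nor refuted. It can be solved backwards:

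- Paired t-test, n = 16, two-sided 0.05, power 0.82: standardised difference 0.769.
- SD of the paired difference = 50 / 0.769 = 65.0 mL.
- With correlation 0.86, the SD of a single measurement = 65.0 / √(2 × 0.14) ≈ 123 mL.
- Other readings (normal approximation, one-sided, Wilcoxon efficiency, crossover degrees of freedom) give an SD of the difference from 63 to 78 mL.

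**2. What that SD means for single patients, with a true mean difference of 0 and no SANO effect.**

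- 95% limits of agreement = ±1.96 × 65.0 = ±127 mL.
- Share beyond 50 mL = 2 × [1 − Φ(50/65.0)] = 0.44, or about 8 of 19.

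| SD of difference (mL) | Limits (mL) | Share beyond 50 mL |
|---|---|---|
| 11.6 (protocol, superseded) | ±23 | almost none |
| 40 | ±78 | 21% |
| 65 (implied by the SAP) | ±127 | 44% |
| 80 | ±157 | 53% |

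The two SDs traceable to the documents differ more than five-fold (65.0 / 11.6 = 5.6).

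**3. Does the planned test see opposite shifts?** Simulation of 4,000 trials of 19 patients, noise SD 65 mL, each patient shifted up or down by a fixed amount with probability one half. These shifts are hypothetical.

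| Shift | Wilcoxon not significant | Share beyond 50 mL | Mean CI half-width (mL) | CI wholly within ±50 mL |
|---|---|---|---|---|
| none | 95% | 44% | 31 | 78% |
| ±75 mL | 95% | 68% | 49 | 10% |
| ±100 mL | 95% | 79% | 60 | 1% |

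The test behaves as if there were no effect in all three rows. The interval does respond, by widening.

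**4. Precision of the proposed limits with 19 patients.**

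- SE of one limit = SD × √[1/n + 1.96²/(2(n − 1))] = 65 × √(0.0526 + 0.1067) = 25.9 mL.
- Multiplied by t(18) = 2.10, this gives about ±55 mL around each limit.
- A count of 8 of 19 has an exact 95% CI of about 20% to 67%.

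**The case against.** **The 44% says nothing about SANO.** A reader might infer that SANO moves nearly half the patients by more than 50 mL. The documents do not support that. The SD is back-solved from a calculation based on repeat cystometry, the mean difference was set to 0, and no SANO effect was added. All of the 44% is repeat variation under an assumed SD. The count is also a blunt detector: a SANO effect varying between patients with SD 30 mL raises the SD to √(65² + 30²) = 71.6 mL and the share only to about 48%. This objection stands in full.

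**The design cannot isolate SANO.** With one run per gas there is no Oxygen–Oxygen replicate, so a paired difference combines SANO effect, run order and noise. Comparing the observed correlation with the cited 0.86 would help little: with 19 patients an estimate of 0.86 has an approximate 95% CI of 0.68 to 0.94, and it depends on between-patient spread in an outside sample. This stands, and limits the fix to description.

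**Individual interchangeability is not a declared conclusion.** The study is a pilot, Aim 1 concerns outcome variables, and protocol B4 speaks of outcomes similar to those on oxygen. A reader might infer that the plan intends to declare a SANO UDS interchangeable patient by patient; neither document says so. What remains is that B1 poses the question at patient level and nothing in the SAP text keeps the conclusion to the average.

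**Opposite shifts are not wholly hidden.** Section 3 of the working shows that the group interval widens markedly. This stands too, but the SAP has no rule under which a wide interval would change the conclusion.

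**The 50 mL is borrowed.** It is the difference used for sample size, not a tolerance for one patient. Its use in a count must be labelled as such.

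**Conclusion.** The point holds as a limit on what the planned analysis can support. Every paired UDS comparison in the SAP text measures net shift. A non-significant Wilcoxon test or a pseudo-median near zero therefore bears on the group average and leaves agreement within patients unreported.

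The figures are illustrations. They rest on an SD the SAP does not state, on a two-sided paired t-test reading of its sample size, on normally distributed differences and on a mean difference of 0. Whether disagreement between runs is in fact large is unknown: the SDs of 11.6 and 65 mL give opposite pictures. Nothing here shows that SANO changes any patient's result. The absence of an agreement analysis is judged on the SAP text available.

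**What to change.** 1. For MCC, Qmax and Pdet max, add a Bland-Altman plot of the paired runs with 95% limits of agreement and their CIs. Allow for run order, for example by marking the two sequences on the plot and basing the limits on the within-sequence SD.
2. Report descriptively the number of patients whose MCC differs by more than 50 mL between runs, by direction, with an exact CI. State that 50 mL is taken from the sample-size calculation.
3. Cross-tabulate the detrusor contraction findings on the SANO run against those on the Oxygen run in the same patient.
4. State that, with one run per gas, the observed differences combine SANO effect, run order and ordinary repeat variation and are not estimates of a SANO effect.
5. Word the Aim 1 conclusion as applying to the group average, not to interchangeability in individual patients.

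The SAP reports its analyses in the past tense, so these additions should be labelled as descriptive and added afterwards.

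**Cost.** A few lines of analysis on data already collected, with no new patients or measurements. With 19 patients each limit is imprecise (about ±55 mL at an SD of 65 mL), and the conclusion becomes more modest.
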